Table 14.2.9.16	SDQ Subscale Peer Relationship Problem Score Change from Baseline at 3 Weeks Double Blind – MMRM Analysis	FAS Set
Table 14.2.9.17	SDQ Subscale Peer Relationship Problem Score and Change from Baseline – Open Label - Descriptive Statistics	FAS Set
Table 14.2.9.18	SDQ Subscale Peer Relationship Problem Score Change from Baseline Analysis During the Open Label Phase	FAS Set
Table 14.2.9.19	SDQ Subscale Prosocial Behaviour Score Change from Baseline at 3 Weeks Double Blind – MMRM Analysis	FAS Set
Table 14.2.9.20	SDQ Subscale Prosocial Behaviour Score and Change from Baseline – Open Label - Descriptive Statistics	FAS Set
Table 14.2.9.21	SDQ Subscale Prosocial Behaviour Score Change from Baseline Analysis During the Open Label Phase	FAS Set
Table 14.2.10.1	ESS Caregiver Sleepiness Score and Change from Baseline – Double Blind - Descriptive Statistics	FAS Set
Table 14.2.10.2	ESS Caregiver Sleepiness Score Change from Baseline at 13 Weeks Double Blind – MMRM Analysis	FAS Set
Table 14.2.10.3	ESS Caregiver Sleepiness Score Change from Baseline at 3 Weeks Double Blind – MMRM Analysis	FAS Set
Table 14.2.10.4	ESS Caregiver Sleepiness Score and Change from Baseline – Open Label - Descriptive Statistics	FAS Set
Table 14.2.10.5	ESS Caregiver Sleepiness Score Change from Baseline Analysis During the Open Label Phase	FAS Set
Table 14.2.11.1	PSQI Global Score and Change from Baseline – Double Blind - Descriptive Statistics	FAS Set
Table 14.2.11.2	PSQI Global Score Change from Baseline at 13 Weeks Double Blind – MMRM Analysis	FAS Set
Table 14.2.11.3	PSQI Global Score Change from Baseline at 3 Weeks Double Blind – MMRM Analysis	FAS Set
Table 14.2.11.4	PSQI Global Score and Change from Baseline – Open Label - Descriptive Statistics	FAS Set

Table Number	Table Title	Population
Table 14.2.11.5	PSQI Global Score Change from Baseline Analysis During the Open Label Phase	FAS Set
Table 14.2.11.6	PSQI Component Scores and Change from Baseline – Descriptive Statistics	FAS Set
Table 14.2.12.1	WHO-5 Well-Being Index Score and Change from Baseline – Double Blind - Descriptive Statistics	FAS Set
Table 14.2.12.2	WHO-5 Well-Being Index Score Change from Baseline at 13 Weeks Double Blind – MMRM Analysis	FAS Set
Table 14.2.12.3	WHO-5 Well-Being Index Score Change from Baseline at 3 Weeks Double Blind – MMRM Analysis	FAS Set
Table 14.2.12.4	WHO-5 Well-Being Index Score and Change from Baseline – Open Label - Descriptive Statistics	FAS Set
Table 14.2.12.5	WHO-5 Well-Being Index Score Change from Baseline Analysis During the Open Label Phase	FAS Set
Table 14.2.13.1	Actigraphy Shift in Time to Bed by Scheduled Visit	FAS Set
Table 14.2.13.2	Number of Responders as per Actigraphy during the Run-In Period	All Enrolled Set
Table 14.2.14.1	SND Total Sleep Time Change from Baseline at 13 Weeks Double Blind – MI Analysis	All Randomized Set
Table 14.2.14.2	SND Sleep Latency Change from Baseline at 13 Weeks Double Blind – MI Analysis	All Randomized Set
Table 14.2.14.3	SND Duration of Wake Change from Baseline at 13 Weeks Double Blind – MI Analysis	All Randomized Set
Table 14.2.14.4	SND Number of Awakenings Change from Baseline at 13 Weeks Double Blind – MI Analysis	All Randomized Set
Table 14.2.14.5	SND Longest Sleep Duration Change from Baseline at 13 Weeks Double Blind – MI Analysis	All Randomized Set
Table 14.2.14.6	SND Total Sleep Time Change from Baseline at 13 Weeks Double Blind – BOCF Analysis	All Randomized Set
Table 14.2.14.7	SND Sleep Latency Change from Baseline at 13 Weeks Double Blind – BOCF Analysis	All Randomized Set
Table 14.2.14.8	SND Duration of Wake Change from Baseline at 13 Weeks Double Blind – BOCF Analysis	All Randomized Set
Table 14.2.14.9	SND Number of Awakenings Change from Baseline at 13 Weeks Double Blind – BOCF Analysis	All Randomized Set
Table 14.2.14.10	SND Longest Sleep Duration Change from Baseline at 13 Weeks Double Blind – BOCF Analysis	All Randomized Set
Table 14.2.14.11	SND Total Sleep Time Change from Baseline at 13 Weeks Double Blind – MMRM Analysis including Geographic Region as a Factor	FAS Set
Table 14.2.14.12	SND Total Sleep Time Change from Baseline at 13 Weeks Double Blind – MMRM Analysis including Center as a Factor	FAS Set
Table 14.2.14.13	SND Total Sleep Time Change from Baseline at 13 Weeks Double Blind – MMRM Analysis including Age as a Factor	FAS Set
Table 14.2.14.14	SND Total Sleep Time Change from Baseline at 13 Weeks Double Blind – MMRM Analysis including Gender as a Factor	FAS Set

Table Number	Table Title	Population
Table 14.2.14.15	SND Total Sleep Time Change from Baseline at 13 Weeks Double Blind – MMRM Analysis including ADHD as a Factor	FAS Set
Table 14.2.14.16	SND Total Sleep Time Change from Baseline at 13 Weeks Double Blind – MMRM Analysis including Autism Type as a Factor	FAS Set
Table 14.2.14.17	SND Total Sleep Time Change from Baseline at 13 Weeks Double Blind – MMRM Analysis including Epilepsy as a Factor	FAS Set
Table 14.2.14.18	SND Total Sleep Time Change from Baseline at 13 Weeks Double Blind – MMRM Analysis including Prior Anti-Epileptic Treatment as a Factor	FAS Set
Table 14.2.14.19	SND Total Sleep Time Change from Baseline at 13 Weeks Double Blind – MMRM Analysis including Prior Anti-Depressant Treatment as a Factor	FAS Set
Table 14.2.14.20	SND Total Sleep Time Change from Baseline at 13 Weeks Double Blind – MMRM Analysis including Prior Beta-Blocker Use as a Factor	FAS Set
Table 14.2.14.21	SND Total Sleep Time Change from Baseline at 13 Weeks Double Blind – MMRM Analysis including Prior ADHD Treatment as a Factor	FAS Set
Table 14.2.14.22	SND Total Sleep Time Change from Baseline at 13 Weeks Double Blind – MMRM Analysis including Prior Clonidine Use as a Factor	FAS Set
Table 14.2.15.1	CSDI Sleep Disturbance Change from Baseline at 13 Weeks Double Blind – MMRM Analysis including ADHD as a Factor	FAS Set
Table 14.2.15.2	CSDI Sleep Disturbance Change from Baseline at 13 Weeks Double Blind – MMRM Analysis including Epilepsy as a Factor	FAS Set
Table 14.2.15.3	CSDI Sleep Disturbance Change from Baseline at 13 Weeks Double Blind – MMRM Analysis including Prior ADHD Treatment as a Factor	FAS Set
Table 14.2.15.4	CSDI Sleep Disturbance Change from Baseline at 13 Weeks Double Blind – MMRM Analysis including Prior Clonidine Use as a Factor	FAS Set
Table 14.2.16.1	CGAS Score Change from Baseline at 13 Weeks Double Blind – MMRM Analysis including ADHD as a Factor	FAS Set
Table 14.2.16.2	CGAS Score Change from Baseline at 13 Weeks Double Blind – MMRM Analysis including Epilepsy as a Factor	FAS Set
Table 14.2.16.3	CGAS Score Change from Baseline at 13 Weeks Double Blind – MMRM Analysis including Prior ADHD Treatment as a Factor	FAS Set

Table Number	Table Title	Population
Table 14.2.16.4	CGAS Score Change from Baseline at 13 Weeks Double Blind – MMRM Analysis including Prior Clonidine Use as a Factor	FAS Set
Table 14.2.17.1	SDQ Total Difficulties Score Change from Baseline at 13 Weeks Double Blind – MMRM Analysis including ADHD as a Factor	FAS Set
Table 14.2.17.2	SDQ Total Difficulties Score Change from Baseline at 13 Weeks Double Blind – MMRM Analysis including Epilepsy as a Factor	FAS Set
Table 14.2.17.3	SDQ Total Difficulties Score Change from Baseline at 13 Weeks Double Blind – MMRM Analysis including Prior ADHD Treatment as a Factor	FAS Set
Table 14.2.17.4	SDQ Total Difficulties Score Change from Baseline at 13 Weeks Double Blind – MMRM Analysis including Prior Clonidine Use as a Factor	FAS Set
Table 14.2.18.1	SND Total Sleep Time and Change from Baseline – Double Blind - Descriptive Statistics by Final Dose	FAS Set
Table 14.2.18.2	SND Sleep Latency and Change from Baseline – Double Blind - Descriptive Statistics by Final Dose	FAS Set
Table 14.2.18.3	SND Duration of Wake and Change from Baseline – Double Blind - Descriptive Statistics by Final Dose	FAS Set
Table 14.2.18.4	SND Number of Awakenings and Change from Baseline – Double Blind - Descriptive Statistics by Final Dose	FAS Set
Table 14.2.18.5	SND Longest Sleep Period and Change from Baseline – Double Blind - Descriptive Statistics by Final Dose	FAS Set
Table 14.2.18.6	SND Total Sleep Time and Change from Baseline – Open Label - Descriptive Statistics by Final Dose	FAS Set
Table 14.2.18.7	SND Sleep Latency and Change from Baseline – Open Label - Descriptive Statistics by Final Dose	FAS Set
Table 14.2.18.8	SND Duration of Wake and Change from Baseline – Open Label - Descriptive Statistics by Final Dose	FAS Set
Table 14.2.18.9	SND Number of Awakenings and Change from Baseline – Open Label - Descriptive Statistics by Final Dose	FAS Set
Table 14.2.18.10	SND Longest Sleep Period and Change from Baseline – Open Label - Descriptive Statistics by Final Dose	FAS Set
Table 14.2.19	Summary of Level of Agreement between Sleep and Nap Diary and Actigraphy Assessment of Responder	FAS Set
Table 14.3.1.1	Summary of Study Drug Exposure	Safety Set
Table 14.3.1.2	Summary of Study Drug Modifications	Safety Set
Table 14.3.1.3	% Compliance by Scheduled Visit	Safety Set
Table 14.3.1.4	Dosage Achieved by Scheduled Visit	Safety Set
Table 14.3.1.5	Number of Dropouts -Chi-Square Test	Safety Set
Table 14.3.2.1	Summary of TESS by Scheduled Visit	Safety Set

Table Number	Table Title	Population
Table 14.3.2.2	Overall Adverse Event Summary: Double Blind Phase	Safety Set
Table 14.3.2.3	Overall Adverse Event Summary: Open Label Phase	Safety Set
Table 14.3.2.4	Treatment Emergent Adverse Events by System Organ Class and Preferred Term: Double Blind Phase	Safety Set
Table 14.3.2.5	Treatment Emergent Adverse Events by System Organ Class and Preferred Term: Open Label Phase	Safety Set
Table 14.3.2.6	Serious Adverse Events by System Organ Class and Preferred Term: Double Blind Phase	Safety Set
Table 14.3.2.7	Serious Adverse Events by System Organ Class and Preferred Term: Open Label Phase	Safety Set
Table 14.3.2.8	Treatment Related Adverse Events by System Organ Class and Preferred Term: Double Blind Phase	Safety Set
Table 14.3.2.9	Treatment Related Adverse Events by System Organ Class and Preferred Term: Open Label Phase	Safety Set
Table 14.3.2.10	Treatment Emergent Adverse Events by System Organ Class, Preferred Term and Severity: Double Blind Phase	Safety Set
Table 14.3.2.11	Treatment Emergent Adverse Events by System Organ Class, Preferred Term and Severity: Open Label Phase	Safety Set
Table 14.3.2.12	Treatment Emergent Adverse Events Leading to Study Drug Discontinuation by System Organ Class and Preferred Term: Double Blind Phase	Safety Set
Table 14.3.2.13	Treatment Emergent Adverse Events Leading to Study Drug Discontinuation by System Organ Class and Preferred Term: Open Label Phase	Safety Set
Table 14.3.2.14	Treatment Emergent Adverse Events on Active Treatment by System Organ Class and Preferred Term: Cumulative	Safety Set
Table 14.3.2.15	Serious Adverse Events on Active Treatment by System Organ Class and Preferred Term: Cumulative	Safety Set
Table 14.3.2.16	Treatment Emergent Adverse Events Study Drug Discontinuation on Active Treatment by System Organ Class and Preferred Term: Cumulative	Safety Set
Table 14.3.3	Vital Sign Parameters and Change from Baseline – Descriptive Statistics	Safety Set
Table 14.3.4.1	Weight and Change from Baseline – Descriptive Statistics	Safety Set
Table 14.3.4.2	Weight and Change from Baseline by Age Group – Descriptive Statistics	Safety Set
Table 14.3.4.3	Height and Change from Baseline – Descriptive Statistics	Safety Set
Table 14.3.4.4	Height and Change from Baseline by Age Group – Descriptive Statistics	Safety Set
Table 14.3.5.1	BMI and Change from Baseline – Descriptive Statistics	Safety Set
Table 14.3.5.2	BMI and Change from Baseline by Age Group – Descriptive Statistics	Safety Set
Table 14.3.5.3	Shift Table of Change in BMI Weight Status	Safety Set

Table Number	Table Title	Population
Table 14.3.5.4	BMI Change from Baseline at 3 Weeks Double Blind – MMRM Analysis	FAS Set
Table 14.3.5.5	BMI Change from Baseline at 13 Weeks Double Blind – MMRM Analysis	FAS Set
Table 14.3.5.6	BMI Change from Baseline Analysis During the Open Label Phase and Run-Out Period	FAS Set
Table 14.3.5.7	BMI Z-Score and Change from Baseline – Descriptive Statistics	Safety Set
Table 14.3.5.8	BMI Z-Score Change from Baseline at 3 Weeks Double Blind – MMRM Analysis	FAS Set
Table 14.3.5.9	BMI Z-Score Change from Baseline at 13 Weeks Double Blind – MMRM Analysis	FAS Set
Table 14.3.5.10	BMI Z-Score Change from Baseline Analysis During the Open Label Phase and Run-Out Period	FAS Set
Table 14.3.6.1	Summary of Tanner Assessment of Pubertal Development - Staging of Pubic Hair Growth	Safety Set
Table 14.3.6.2	Summary of Tanner Assessment of Pubertal Development - Staging of Breast Development	Safety Set
Table 14.3.6.3	Summary of Tanner Assessment of Pubertal Development - Staging of Genitalia Development	Safety Set
Table 14.3.6.4	SD Score and Change from Baseline - Pubic Hair Growth – Descriptive Statistics	Safety Set
Table 14.3.6.5	SD Score and Change from Baseline - Breast Development – Descriptive Statistics	Safety Set
Table 14.3.6.6	SD Score and Change from Baseline - Genitalia Development – Descriptive Statistics	Safety Set
Table 14.3.7.1	Head Circumference and Change from Baseline – Descriptive Statistics	Safety Set
Table 14.3.7.2	Head Circumference and Change from Baseline by Age Group – Descriptive Statistics	Safety Set
Table 14.3.8.1	Number of Epilepsy Seizures in Children Diagnosed with Epilepsy - Categorical Summary	Safety Set
Table 14.3.8.2	Number of Epilepsy Seizures in Children Diagnosed with Epilepsy - Wilcoxon Rank-Sum Test	Safety Set
Table 14.3.8.3	Type of Epilepsy Seizures in Children Diagnosed with Epilepsy	Safety Set

16.2 List of Figures

Figure Number	Figure Title	Population
Figure 14.2.1.1	Change from Baseline in Mean TST over Time	FAS Set
Figure 14.2.1.2	Change from Baseline in Mean Sleep Latency over Time	FAS Set
Figure 14.2.1.3	Change from Baseline in Mean Duration of Wake over Time	FAS Set
Figure 14.2.1.4	Change from Baseline in Mean Number of Awakenings over Time	FAS Set
Figure 14.2.1.5	Change from Baseline in Mean Longest Sleep Duration over Time	FAS Set
Figure 14.2.1.6	SND Total Sleep Time Change from Baseline at 13 Weeks Double Blind - Empirical Cumulative Distribution Plot	FAS Set
Figure 14.2.1.7	SND Sleep Latency Change from Baseline at 13 Weeks Double Blind - Empirical Cumulative Distribution Plot	FAS Set
Figure 14.2.1.8	SND Duration of Wake Change from Baseline at 13 Weeks Double Blind - Empirical Cumulative Distribution Plot	FAS Set
Figure 14.2.1.9	SND Number of Awakenings Change from Baseline at 13 Weeks Double Blind - Empirical Cumulative Distribution Plot	FAS Set
Figure 14.2.1.10	SND Longest Sleep Duration Change from Baseline at 13 Weeks Double Blind - Empirical Cumulative Distribution Plot	FAS Set
Figure 14.2.2.1	Total Sleep Time, Sleep and Nap Diary against Actigraphy – Bland and Altman Plots	FAS Set
Figure 14.2.2.2	Sleep Latency, Sleep and Nap Diary against Actigraphy – Bland and Altman Plots	FAS Set
Figure 14.2.2.3	Duration of Wake, Sleep and Nap Diary against Actigraphy – Bland and Altman Plots	FAS Set
Figure 14.2.2.4	Number of Awakenings, Sleep and Nap Diary against Actigraphy – Bland and Altman Plots	FAS Set

Figure 14.2.2.5	Longest Sleep Duration, Sleep and Nap Diary against Actigraphy – Bland and Altman Plots	FAS Set
Figure 14.2.3.1	Scatterplot of SND TST versus CSDI	FAS Set
Figure 14.2.3.2	Scatterplot of SND TST versus CGAS	FAS Set
Figure 14.2.3.3	Scatterplot of SND TST versus SDQ Total Score	FAS Set
Figure 14.2.3.4	Scatterplot of SND Sleep Latency versus CSDI	FAS Set
Figure 14.2.3.5	Scatterplot of SND Sleep Latency versus CGAS	FAS Set
Figure 14.2.3.6	Scatterplot of SND Sleep Latency versus SDQ Total Score	FAS Set
Figure 14.2.3.7	Scatterplot of SND WASO versus CSDI	FAS Set
Figure 14.2.3.8	Scatterplot of SND WASO versus CGAS	FAS Set
Figure 14.2.3.9	Scatterplot of SND WASO versus SDQ Total Score	FAS Set
Figure 14.2.4.1	Scatterplot of Actigraphy TST versus CSDI	FAS Set
Figure 14.2.4.2	Scatterplot of Actigraphy TST versus CGAS	FAS Set
Figure 14.2.4.3	Scatterplot of Actigraphy TST versus SDQ Total Score	FAS Set
Figure 14.2.4.4	Scatterplot of Actigraphy Sleep Latency versus CSDI	FAS Set
Figure 14.2.4.5	Scatterplot of Actigraphy Sleep Latency versus CGAS	FAS Set
Figure 14.2.4.6	Scatterplot of Actigraphy Sleep Latency versus SDQ Total Score	FAS Set
Figure 14.2.4.7	Scatterplot of Actigraphy WASO versus CSDI	FAS Set
Figure 14.2.4.8	Scatterplot of Actigraphy WASO versus CGAS	FAS Set
Figure 14.2.4.9	Scatterplot of Actigraphy WASO versus SDQ Total Score	FAS Set

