6.1 INCLUSION CRITERIA

To be eligible for study entry, all patients must satisfy all of the following criteria at screening:

- Must be children 2 to 17.5 years of age at Visit 2 who comply with taking the study drug.
- Must have written informed consent provided by a legal guardian and assent (if needed).
- Must have a documented history of ASD according to or consistent with the ICD-10 or DSM-5/4 criteria, or neurodevelopmental disabilities caused by neurogenetic diseases (SMS, Angelman syndrome, Bourneville's disease [tuberous sclerosis]) as confirmed by case note review showing that diagnosis was reached through assessment by a community pediatrician or pediatric neurologist or other health care professionals experienced in the diagnosis who took into account early developmental history and school records.
- Must have current sleep problems including: a minimum of 3 months of impaired sleep defined as ≤ 6 hours of continuous sleep AND/OR ≥ 0.5 hour sleep latency from light off in 3 out of 5 nights based on parent reports and patient medical history. (The maintenance and latency problems do not necessarily have to be in the same 3 nights of the week.)
- May be on a stable dose of non-excluded medication for 3 months, including anti-epileptics, anti-depressants (selective serotonin reuptake inhibitors [SSRIs]), stimulants, all mood changing drugs and β -blockers. (Only morning administration of β -blockers is allowed since β -blockers at night have the potential to reduce endogenous melatonin levels and might cause disturbed sleep).
- The sleep disturbance is not due to the direct physiological effects of any concomitant medications such as SSRIs, stimulants, etc.

After completing 4 weeks of sleep hygiene training (for those who need it) and 2 weeks of placebo run-in, patients will be eligible to continue the study if they comply with the following:

- Continue to fulfil sleep problem criteria (see Inclusion Criterion 4) based on the completed Sleep and Nap Diary entered into the electronic case report form (eCRF)

- Parents demonstrate compliance in Sleep and Nap Diary completion (5 out of 7 nights). Compliance means that in at least 5 out of 7 nights per week (total of 2 weeks before each scheduled visit) the parents complete the diary pages with all mandatory questions (mandatory questions are marked with an asterisk [*] in [Appendix 1](#)).
- Continue to fulfil all other eligibility criteria

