6.1 Sample Size

To achieve 95% power at the 5% level for the primary objective (assuming a change of 0.72 hour in the Circadin® arm and 0.27 hour in the placebo arm and a standard deviation (SD) of 0.69 in the Circadin® arm and 0.45 in the placebo arm), 45 subjects are required per combined group. Therefore, 90 subjects in total are required to complete Visit 5. These estimations are based on previous studies conducted with Circadin®.

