11.7 Agreement between Sleep and Nap Diary and Actigraphy

An analysis will be performed to assess the agreement of the following sleep parameters collected via the Sleep and Nap Diary and actigraphy:

- Total Sleep Time
- Sleep Latency
- Duration of Wake
- Number of Awakenings
- Longest Sleep Duration
- Total Time in Bed
- Number of Responders at baseline, Visit 2 (defined as > 6 hours of continuous sleep and < 0.5 hour sleep latency from light off in 3 out of 5 nights.)

The analysis will use data from Visits 2 and 4. Agreement will be assessed using the methods described by Bland and Altman ([4], [5]). Bland and Altman plots (plotting the difference in the measurements from the two sources versus the average of the measurements from the two sources) will be produced and the 95% limits of agreement calculated.

Example SAS code for the calculation of the limits of agreement is given below:

```
proc mixed data=agree method=type1;  
class subjid;  
model diff=/solution ddfm=sat;  
random subjid;  
ods output CovParms=covparms;  
run;  
  
proc means data=agree noprint;  
var diff;  
output out=meandiff mean=meandiff;  
run;
```

```
data loa;  
  merge meandiff covparms(where=(covparm='SUBJID') rename=(estimate=between))  
covparms(where=(covparm='Residual') rename=(estimate=within));  
  std=sqrt(within+between);  
  upper_loa=meandiff+(1.96*std);  
  lower_loa=meandiff-(1.96*std);  
run;
```

For number of responders, a 2 x 2 table will be presented tabulating responders according to the sleep and nap diary against responders according to actigraphy. Agreement between the sleep and nap diary and actigraphy responders will be summarised using Cohen's kappa statistic. The hypothesis that Cohen's kappa differs from 0 will be tested. A 95% confidence interval for Cohen's kappa will also be presented.

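### The diary–actigraphy agreement analysis gives one bias and one pair of limits across Visits 2 and 4 and both arms, so any shift in the gap by visit or arm would be diluted

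*SAP*

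**What the plan says.** SAP 11.7 plans a Bland–Altman comparison of diary and actigraphy: "The analysis will use data from Visits 2 and 4". The example code fits the diary-minus-actigraphy difference with an intercept only, "model diff=/solution ddfm=sat", and one random effect, "random subjid". The bias is a single mean over all records, "output out=meandiff mean=meandiff". The SD for the limits is "std=sqrt(within+between"), and the limits are the mean ± 1.96 times that SD. There is no visit term, treatment term, BY statement or subset.

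SAP 16.2 gives one figure number per parameter (Figures 14.2.2.1 to 14.2.2.5). The TST title, "Total Sleep Time, Sleep and Nap Diary against Actigraphy – Bland and Altman Plots", names no visit and no arm. The rule in SAP 9.2 on presenting double-blind results by treatment group refers to tables. The only agreement item tied to a visit is the responder comparison at Visit 2.

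Elsewhere the SAP reports diary TST (Tables 14.2.1.3 and 14.2.1.4) and actigraphy TST (Tables 14.2.5.1 and 14.2.5.2) separately, each with descriptive statistics and a Week 15 MMRM. Listing 16.2.6.4 shows both sources.

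**The concern.** The model treats a child's Visit 2 and Visit 4 differences as replicates with the same expected value. The design gives reasons to doubt that.

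- Protocol 7.4 puts every child on placebo in the run-in, so a drug-related difference between arms can appear only at Visit 4.
- Children go on to randomisation only if they "Continue to fulfil sleep problem criteria (see Inclusion Criterion 4) based on the completed Sleep and Nap Diary". Selecting on the diary and not on actigraphy makes regression to the mean in the diary plausible, which would move the gap in both arms.
- Parents estimate sleep latency and night waking, and these enter the diary TST (SAP 11.1.1).

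Parent-reported diary TST is the primary endpoint. Actigraphy is the only objective measure of the same quantity and is worn only before Visits 2 and 4 (Protocol Section 8). The useful question is whether the gap changed between those visits, and whether it changed differently under Circadin. The pooled figure cannot answer it.

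**Working it through.** **The plan's own figures.** The SAP states no numerical bias or limits for agreement. SAP 6.1 supplies the cell size and a scale: "assuming a change of 0.72 hour in the" Circadin arm, 0.27 h on placebo, SDs 0.69 and 0.45 h, 95% power, 5% level, 45 per group.

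- Normal approximation: (1.960 + 1.645)² × (0.69² + 0.45²) / 0.45² = 12.995 × 0.6786 / 0.2025 = 43.5, so 44 per group.
- With the t distribution, 44 gives 94.8% power and 45 gives 95.2%, so 45 is reproduced.
- Planned treatment difference: 0.72 − 0.27 = 0.45 h = 27 min.

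**Why the code must be pooling.** Each parameter is a 14-day mean, so each child has one difference per visit. Between-child and within-child variance can be separated only if both visits are in the same fit.

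**Bias.** Set the Visit 2 gap to zero. Let v be a Visit 4 shift common to both arms and t an extra shift under Circadin at Visit 4. With equal cells the means are 0, 0, v and v + t, so

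pooled bias = (0 + 0 + v + v + t)/4 = v/2 + t/4.

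- v = 0, t = 0: pooled bias 0, correct in every cell.
- v = 0, t = 0.45 h: 0.45/4 = 0.1125 h = 6.75 min, against 27 min in the affected cell.
- v = 0.5 h, t = 0.45 h: 0.25 + 0.1125 = 0.36 h, against cell values of 0, 0, 0.5 and 0.95 h.
- v = 0, t = 1.0 h: 0.25 h.

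**Limits.** Let S be the SD of the difference within one visit and arm. The documents give none, so I assume 0.61, 0.86 or 1.22 h. In expectation the shifts add [v² + (v + t)²]/4 to the within-child variance, and the squared SD used for the limits becomes

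S² + t²/16 + [v² + (v + t)²]/8.

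For S = 0.86 h (within-child SD 0.50 h), v = 0, t = 0.45 h:

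- Within-child SD: √(0.25 + 0.0506) = 0.55 h.
- SD for the limits: √(0.7396 + 0.0127 + 0.0253) = 0.882 h.
- Limits: 0.1125 ± 1.96 × 0.882 = −1.616 to 1.841 h.
- Circadin at Visit 4: the upper limit is (1.841 − 0.45)/0.86 = 1.617 SD above the cell mean, so 5.3% of children lie above it instead of 2.5%. The lower limit is 2.402 SD below, leaving 0.8%. Coverage is 93.9%.
- The other three cells: 95.4%.

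A simulation of the coded estimator (45 per arm, 4,000 replicates) agrees. Coverage in the Circadin Visit 4 cell over the three values of S:

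| v (h) | t (h) | Pooled bias (h) | Coverage |
|---|---|---|---|
| 0 | 0 | 0 | 95.0% |
| 0 | 0.45 | 0.11 | 92.9–94.4% |
| 0.5 | 0.45 | 0.36 | 91.4–93.7% |
| 0 | 1.0 | 0.25 | 88.0–92.6% |

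The main distortion is in the bias. For moderate shifts the limits change little.

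**Unequal cells.** Assume 60 per arm at Visit 2, 48 per arm at Visit 4, and actigraphy that does not move while the diary moves as planned. The pooled bias is (48 × 0.72 + 48 × 0.27)/216 = 47.52/216 = 0.22 h (13 min). It is off by 30 min for Circadin at Visit 4 (0.72 − 0.22 = 0.50 h), 13 min at Visit 2, and 3 min for placebo at Visit 4 (0.27 − 0.22 = 0.05 h). If actigraphy moves half as much as the diary, each error halves; if it moves equally, each is zero.

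**The case against.** A reader might infer that the pooled bias and limits are wrong for every visit and arm. The documents do not support that. With a constant gap they are right everywhere, and no document gives the gap, its SD or its shift. Even when actigraphy is assumed not to move, the Visit 4 placebo cell is only 3 min off.

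A reader might also infer that the SAP conceals whether the diary over-reports more under Circadin. That is true of these figures but not of the SAP as a whole. The diary and actigraphy tables give both sources, and subtracting one Week 15 MMRM treatment effect from the other estimates the differential over-reporting. A treatment effect absent on actigraphy would be visible in Table 14.2.5.2. That subtraction has no planned CI, however, and children with valid actigraphy may differ from those with valid diaries.

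Other points on that side:

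- The diary instructions (Protocol Appendix 2) tie diary bedtime and wake time to the Actiwatch, which limits how far the two TST values can diverge. Latency and night waking remain parent-estimated.
- The diary retention criterion concerns continuous sleep and latency, so the selection argument is indirect for TST.
- The code is labelled an example, and the plural in the figure titles leaves room for panels. None are specified.
- Agreement is not among the SAP objectives, and no primary or secondary test depends on it.

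These points limit the size and weight of the concern. The pooling, and the absence of any planned paired summary by visit or arm for these parameters, still stand.

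**Conclusion.** The point holds as a conditional weakness in a supportive analysis. As specified, the agreement bias carries half of any common Visit 4 shift and a quarter of any Circadin-only shift, on the assumption of equal cells. A Circadin-only shift as large as the whole planned treatment difference would be reported at a quarter of its size, with coverage in that cell falling only to about 93–94%. All sizes rest on assumed shifts and SDs. The primary test is unaffected. A change is worth making because it is cheap and the check concerns the parent-reported primary endpoint.

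**What to change.** In SAP 11.7 and Figures 14.2.2.1 to 14.2.2.5, give the Bland–Altman plot, mean difference and 95% limits separately for Visit 2 (all children), Visit 4 Circadin and Visit 4 placebo. Take each from that cell's own mean and SD. With one value per child in a cell, no random effect is needed.

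For TST, add a supportive ANCOVA of the Visit 4 diary-minus-actigraphy difference on treatment, with the Visit 2 difference as covariate, and report the Circadin-minus-placebo contrast with its 95% CI.

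Adding visit and treatment-within-visit terms to the present model would not be enough. It would fit an arm effect at Visit 2, keep one common variance for all limits, and leave the Visit 4 contrast without the Visit 2 difference as a covariate.

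The cost is SAP wording and a few lines of SAS on data already collected. The downside is fewer children per plot, so each pair of limits is less precise.
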